	
Secondary Frequency of cerebral desaturation events (CDE) measured (INVOS™ vs FORE-SIGHT®). Cerebral desaturation will be defined as a decrease in rSO2 greater than, or equal to 20% from baseline or a fall below 50% absolute (after Murphy et al., 2010; Salazar et al., 2013). Variables associated with this outcome include:
 
 • Mean Arterial Pressure (mmHg) • BMI • Hypertension • Nausea and Vomiting – within 48 hours • Duration of hospital stay • Adverse Events
--	---

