A number of cerebral oximeters are commercially available. Douds et al. (2014) completed a systematic review of devices commonly used in cardiac surgery and concluded that there were only a very limited number of high quality papers available. Most of these papers were based on the INVOS™ system. These authors highlighted the need for further RCTs to investigate the role of cerebral oximetry and the efficacy of devices currently available. Hessel et al., (2014) examined cerebral oxygenation in newborns using both the FORE-SIGHT® and INVOS™ monitors. They found that the FORE-SIGHT® monitor demonstrated greater repeatability and hypothesised that this may indicate a lower responsiveness to change in oxygen saturation. In contrast, Closhen et al., (2013) compared the use of the INVOS™ and FORE-SIGHT® monitors to detect oxygen saturation in the beach chair position and found no significant difference according to monitor type. The study by Bickler et al., (2013) compared the performance of several cerebral oximeter devices including the FORE-SIGHT® and INVOS™ monitors. It compares the performance of different cerebral oximetry devices using an invasive reference standard and a common sample population (health adult volunteers), simultaneous testing methodology and data analysis. It is important that the monitors are being used within their approved indication for and that care must be taken to avoid optical cross-talk between the sensors of different manufacturers. In addition, the sensors will be placed randomly on the forehead in terms of superior and inferior in the same position to avoid sequential bias. Both the FORE-SIGHT® and INVOS™ cerebral oximetry measurements have been assessed and shown to be valid surrogates for true cerebral oxygenation .

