Monitoring cerebral oxygenation in the BCP is an area of evolving attitudes in regards to standard of care. There are many hospitals in Australia who have now adopted cerebral oximetry as a standard of care for monitoring patients in the beach chair position. It is the feeling of all of the surgeons involved in the investigation that in fact, cerebral oxygenation monitoring is part of an adequate standard of care for patients in the beach chair position and it is routinely utilised currently in all beach chair position surgeries. It is not expected that there will be any significant alteration to operative time by placing two oxygen monitors and there is certainly no risk to the surgeon, anaesthetist or the nursing team. Data is recorded using monitors that output the data digitally and all of the data will be compared using standard timestamp methods so that they can be directly compared. The oximetry and MAP data will be simultaneously digitally recorded for the research data collection and analyses.

In conclusion, the relationship between shoulder surgery in the BCP and cerebral oxygenation is suggestive and requires further investigation. In addition, factors associated with cerebral desaturation and the incidence of POCD are not well understood. The value of cerebral oximetry in predicting CDE and POCD remains unclear. Further research in these areas is indicated and the proposed study aims to address the issues raised here.

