7.2.3 DATA COLLECTION FORMS FOR PRIMARY AND SECONDARY HYPOTHESES

Primary and secondary outcomes will be recorded for each participant on their data collection form. This form will include demographic, clinical and outcome data (24.4). The primary outcome to be measured is the incidence of Post-operative Cognitive Decline. This has been defined as a drop of 1 standard deviation or more from baseline on 2 or more of the neuropsychological indices included. The secondary outcome to be measured is the incidence of cerebral desaturation as well as the importance of other key clinical variables (e.g. blood pressure, nausea, body fat etc).

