10.1 STATISTICAL METHODS

Baseline demographic and clinical data will be examined using descriptive statistics (means, standard deviations [SDs], and percentages). Dropouts will be compared to those who complete the study. For initial data screening, descriptive statistics (means, standard deviations [SDs], and percentages) will be completed for all predictor and outcome variables. Based on the findings of de Tournay - Jette et al. (2011), we assume that 62% of patients will not experience desaturation, and that the probability of postoperative cognitive dysfunction in these patients is 29%. To observe an increased risk of cognitive dysfunction of 1.75 times in patients who experienced desaturation (i.e. to 50%) we will be required to collect postoperative data on 193 participants, assuming $\alpha=0.05$ and $\text{power}=80\%$. For the secondary outcome, which is the concordance between the INVOS™ 5100 and FORE-SIGHT® devices during shoulder surgery, the agreement between these pairs of observations will be assessed using intra-class correlation (ICC 3,1) (Portney & Watkins, 1993).

A number of statistical analyses will be used to explore the relationship between CDE and other study variables to allow for use of continuous and categorical data (e.g. linear & logistic regression). With an anticipated sample size of 200 this should provide adequate numbers for our analysis (Portney & Watkins, 1993). Prior to the use of a regression analysis, exploratory bivariate analyses (e.g. correlation, chi square, one-way ANOVA) will be conducted among all predictor variables to identify multi-collinearity. Bivariate analyses between each predictor and outcome variable will then be conducted. Significant predictor variables identified from bivariate analyses will be entered into the regression model. A process of backward elimination will then be used to identify the best model considering main effects and two-way interactions at $p \leq 0.05$. Data analysis will be conducted using SSPS version 23. Any complication rates will be reported in terms of frequency and analysed. The potential contribution of type of surgery, the length of surgery and the nature of the anaesthetic agents

used are recorded as standard practice and will be included in analyses to assess whether or not they represent confounding factors. The final multivariable model will include the main effects of interest and variables identified as potential confounders.

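### The secondary outcome is how often each oximeter records a desaturation event, but the one between-device analysis named is ICC(3,1), which does not compare event frequency

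*Protocol*

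**What the plan says.** - Section 1, secondary outcomes: "Frequency of cerebral desaturation events (CDE) measured (INVOS™ vs FORE-SIGHT"). The event is a threshold crossing: "Cerebral desaturation will be defined as a decrease in rSO2 greater than, or equal to 20% from baseline or a fall below 50% absolute".
- Section 7.2.3: "The secondary outcome to be measured is the incidence of cerebral desaturation", together with other clinical variables. It mentions no comparison of devices.
- Section 8.2: CDE are recorded from both machines, and software captures their number, depth and duration. Sub-analyses of these features are optional.
- Section 10.1: "For the secondary outcome, which is the concordance between the INVOS™ 5100 and FORE-SIGHT® devices during shoulder surgery", followed by "the agreement between these pairs of observations will be assessed using intra-class correlation (ICC 3,1"). What forms a pair is not defined. The regression paragraph relates CDE to other variables, not one device to the other. Descriptive statistics, including percentages, are planned for every predictor and outcome.
- Aim (ii) in section 3.3 and the hypotheses in sections 3.5 and 3.6 concern measured oxygenation. The research hypothesis expects the two monitors not to differ significantly.
- Section 2 reports that greater FORE-SIGHT repeatability in newborns "may indicate a lower responsiveness to change in oxygen saturation". It then cites a beach-chair comparison of the same monitors that found no significant difference.

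**The concern.** The outcome in section 1 and the statistic in section 10.1 answer different questions. Whether two monitors flag the same patients at a threshold is a matter of paired classification. ICC(3,1) is a consistency coefficient: it removes the device main effect before judging agreement. A constant offset therefore leaves it unchanged, although an offset alters who falls below 50% and how many points make up 20% of baseline. For the same reason it cannot test the hypothesis of no difference between monitors.

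The study could report excellent agreement while the monitors disagree on who desaturated. CDE status is also the exposure in the primary question, and its definition is not tied to one device. A hidden disagreement would bear on the reading of the primary result too.

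**Working it through.** The plan gives no figure for the device comparison that could be reproduced. Its one computed sample size, 193, belongs to the primary comparison and is not at issue.

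**Inputs.** The CDE rule is from sections 1 and 8.2. The documents give no rSO2 mean, SD, noise or responsiveness, so these are assumptions: baseline B with mean 68 and SD 7; fall D on the first device with mean 11 and SD 6, independent of B; reading noise with SD s on each device; a second device that shows a fraction r of the fall and has a constant offset c.

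**ICC(3,1) on the lowest readings.** Device 1 reads B − D + noise; device 2 reads B + c − rD + noise. For two devices:

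ICC(3,1) = (BMS − EMS)/(BMS + EMS) = 2·cov/(var1 + var2) = 2(49 + 36r) / [(85 + s²) + (49 + 36r² + s²)]

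The offset c does not appear.

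- r = 0.70: 148.4/(151.64 + 2s²). With s = 1, 148.4/153.64 = 0.97; s = 2, 148.4/159.64 = 0.93; s = 3, 148.4/169.64 = 0.87.
- r = 0.85: 159.2/(160.01 + 2s²). With s = 1, 159.2/162.01 = 0.98; s = 2, 159.2/168.01 = 0.95.

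**CDE on each device.** Simulating these inputs and applying the protocol's rule to each device:

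| Responsiveness | Offset | Noise SD | ICC(3,1) | CDE, device 1 | CDE, device 2 |
|---|---|---|---|---|---|
| 70% | 0 | 1–2 | 0.93–0.97 | about 38% | 15–17% |
| 85% | 0 | 1–2 | 0.95–0.98 | 38–39% | 27–28% |
| 85% | 5 points | 1–2 | essentially unchanged | 38–39% | 18–20% |
| 70% | 0 | 3 | 0.87 | ratio of device 2 to device 1 about 0.5 | |

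In the first row kappa is about 0.45. In 200 patients that row means about 0.38 × 200 = 76 with CDE on one device and 30 to 34 on the other.

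**Other assumed inputs.** With between-patient SD 8, noise SD 1.5, no offset and r = 0.7, ICC(3,1) is 0.96 in two settings: first-device CDE of 18% (the incidence cited in section 2) with 7.8% on the second, and 38% (the complement of the 62% in section 10.1) with 16.0%. Absolute-agreement ICC(2,1) in these two settings stays at 0.90 to 0.94, so changing the form of ICC alone is no remedy. With between-patient SD 6 and noise SD 2.5, ICC(3,1) was often 0.86 to 0.89. With an 8-point offset alone and 38% CDE, the ratio was 0.61 to 0.68.

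**If the pairs are something else.** With the main inputs at r = 0.7 and noise SD 1 to 2, ICC(3,1) is 0.71 to 0.87 on falls from baseline and about 0.5 on a per-patient CDE indicator.

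**The case against.** The strongest reply is that an agreement statistic on oxygenation fits aim (ii) and its hypotheses, so the fault is mainly one of labelling. That stands in part: agreement of rSO2 deserves an analysis. It does not supply the comparison that section 1 names, and ICC(3,1) cannot show a systematic difference between monitors.

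The undefined pair is also a fair point. Computed on CDE indicators, the ICC would be low and would reveal disagreement between devices. The result for readings is therefore conditional, though even on indicators ICC(3,1) would still disregard a difference in mean frequency.

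Descriptive percentages would show a marginal gap such as 38% against 16%. They would not show which patients are discordant, nor give an interval for the paired difference.

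The responsiveness concern rests on a hypothesis from newborns, and the beach-chair study cited next points the other way. The documents do not show that these devices differ. The finding is that the named analysis could miss it if they do.

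Three stronger readings are tempting and unsupported:

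- A reader might infer from "all of the data will be compared using standard timestamp methods so that they can be directly compared" that all time points will be pooled as independent pairs, making the interval for the ICC far too narrow. The protocol does not say so. With one pair per patient there is no clustering, and any inflation factor would need a number of pairs and an autocorrelation that the documents do not give.
- A reader might take section 7.2.3 as a second definition of a device comparison. It speaks only of the incidence of desaturation.
- A reader might treat a yes/no status per patient as the stated endpoint. Section 1 says frequency, and section 8.2 allows for counts and durations. The patient-level split is, however, how section 10.1 frames its sample size.

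**Conclusion.** The point holds as a mismatch between outcome and analysis. It is not a detail left to a later plan, because section 10.1 fixes a statistic for the secondary outcome and that statistic does not compare CDE between devices. That the offset drops out of ICC(3,1) follows from its definition and needs no assumption. How far a high ICC can coexist with different CDE rates depends wholly on assumed inputs and on the pairs being rSO2 readings. An ICC above 0.9 with fewer than half the events is possible, not general: at 85% responsiveness without offset the CDE ratio is about 0.7 (27/38 = 0.71), and with noise SD 3 at 70% the ICC is below 0.9. The change should be made, but the planned size of the study does not turn on it.

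**What to change.** 1. Reconcile sections 1 and 10.1 so that both name the same secondary outcome, and state what a pair of observations is.
2. In section 10.1, classify each patient as CDE yes or no on each device from the synchronised record. Report the paired 2×2 table, the difference in incidence with a 95% CI, McNemar's test and kappa.
3. Keep agreement of rSO2 as support. Report mean bias and limits of agreement, both on readings and on change from each device's own baseline, instead of ICC(3,1) alone.
4. If several time points per patient enter the agreement analysis, account for clustering by patient.

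The cost is some wording in two sections and a few lines of code. Both devices are already recorded digitally, so no new data are needed.

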Battery for Assessment of Neuropsychological Status “(RBANS) with either composite scores or using the sub-indices. They attribute this lack of significant findings to insufficient study power. The incidence of cerebral desaturation in their study was 18% (9/50 participants). In contrast, de Tournay-Jette et al, (2011) found a significant relationship between CDE and POCD in elderly patients following coronary artery bypass graft surgery. These authors used a detailed battery of neuropsychological assessments and highlight the need for sensitive assessments of cognitive function.

This difficulty in clarifying the relationship between CDE and POCD may be further compounded by our ability to accurately measure cerebral perfusion. To date, no clear definition of cerebral ischaemia exists and little is known about individual patient factors (e.g. pre-existing cerebral vascular disease) that may influence cognitive outcome (Murphy et al., 2010). Additionally, changes in the proportion of venous versus arterial components of blood pressure will vary with changes in body position. This is not necessarily reflected in the observed change in overall oxygen concentration (Murphy et al., 2010). Individual variation in acceptable mean arterial blood pressure has also been reported. Whilst 50mmHg is generally the accepted level, the required level in some cases has been found to be as high as 70-80mmHg (Murphy et al., 2010). Hence, the conditions leading up to a CDE associated with cognitive impairment may vary from one patient to another and are influenced by patient specific characteristics (Murphy et al., 2010).

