5.5 SAMPLE SIZE

Approximately 200 participants will be recruited to the study. Based on historical patient presentation rates for this group, it is anticipated that recruitment will take approximately 24 months. This allows for 75% recruitment rate and 30% loss to follow up.

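### Section 10.1 calls the regressions adequate from a total of 200, but POCD events (about 52–71) set the limit, and the planned selection from an unlisted candidate set often keeps spurious predictors

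*Protocol*

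**What the plan says.** Section 10.1 of the protocol first gives a sample-size calculation for the unadjusted comparison of POCD between patients with and without CDE, which needs 193 participants with post-operative data. It then turns to linear and logistic regressions relating CDE to other study variables. For these it offers only total sample size and a textbook citation: "With an anticipated sample size of 200 this should provide adequate numbers for our analysis". It counts neither events nor predictors.

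The same section fixes how models are built. Each predictor is tested against each outcome, the significant ones enter a regression, and backward elimination is used to "identify the best model considering main effects and two-way interactions" at p ≤ 0.05. Surgery type, surgery length and anaesthetic agents are to be examined as confounders. The final model is to contain the main effects of interest and any confounders identified.

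Section 5.5 says of the 200 recruited: "This allows for 75% recruitment rate and 30% loss to follow up". No section lists the candidate predictors. Section 7.2.2 describes an open-ended set of demographic and medical items, and section 8.1.2 says the psychological measures are included so that they can be adjusted for.

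**The concern.** POCD and CDE are both defined as yes/no events (sections 7.2.3 and 8.2). The information in a logistic model is governed by the smaller outcome class, so a statement of adequacy based on 200 participants does not address the question.

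The selection procedure adds to this. When many candidates are screened at p ≤ 0.05 on the same data, and interactions are then searched, some variables enter by chance and the model looks better in the sample than it is. The study's title promises prediction of POCD, and section 13 expects the findings to guide models of care. Readers would therefore take a reported predictor set and its discrimination at face value.

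**Working it through.** **The plan's own figure.** Inputs from section 10.1: 62% without CDE, POCD 29% without CDE and 50% with it, α = 0.05 (taken as two-sided), power 80%. Put k = 0.38/0.62 = 0.613, d = 0.21 and p̄ = 0.62 × 0.29 + 0.38 × 0.50 = 0.3698.

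- n without CDE = [1.96 √((1 + 1/k) p̄(1 − p̄)) + 0.8416 √(0.29 × 0.71 + 0.25/k)]² / d² = (1.535 + 0.659)² / 0.0441 ≈ 109.2, so 110. The total is 110/0.62 ≈ 178.
- With continuity correction, 122 without CDE; 122/0.62 ≈ 197.

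The stated 193 lies within about 2% of the corrected figure (197/193 = 1.02). That calculation covers only the unadjusted two-group comparison, not the regressions.

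**Evaluable patients.** The upper case is the required 193. The lower case is 200 × 0.70 = 140, assuming the 30% loss applies to the 200 recruited.

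**Events** (N × rate):

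| Outcome and rate | N = 140 | N = 193 |
|---|---|---|
| POCD, 37.0% (CDE at 38%) | 52 | 71 |
| POCD, 0.82 × 0.29 + 0.18 × 0.50 = 32.8% (CDE at 18%) | 46 | 63 |
| CDE at the planning rate, 38% | 53 | 73 |
| CDE at 18% | 25 | 35 |

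The 38% is the complement of the 62% in section 10.1, taken from a cardiac surgery study. The 18% (9 of 50) is what section 2 reports for the beach-chair study of CDE and cognition.

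**Events per candidate main effect.** The number of candidates is not stated, so 10 to 20 is an assumption. For POCD, 20 candidates give 52/20 = 2.6 to 71/20 = 3.6 events each; 10 candidates give 5.2 to 7.1.

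**Rough check on screening.** If all candidates other than CDE are null and independent, the chance that at least one passes at 0.05 is 1 − 0.95⁹ = 37% with 10 candidates and 1 − 0.95¹⁹ = 62% with 20. Backward elimination should then remove some of these.

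**Simulation of the planned sequence.** Settings: CDE 38%, POCD 29% and 50% (odds ratio 0.71/0.29 = 2.45), all other covariates null, about half of them mildly correlated with CDE. Steps: bivariate screening at 0.05, then backward elimination, with CDE retained. Results for N = 140 to 193:

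- The final model held 1.3–1.8 parameters on average.
- Bias in the CDE log odds ratio was within about 2%, and 95% intervals covered in 93–95% of runs.
- At least one spurious term was present in 27–30% of final models with 10 candidates and in 47–50% with 20.
- With 20 candidates the apparent AUC was about 0.64–0.65, against 0.59–0.60 in new patients.

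**The case against.** **The planned models are small.** A reader might infer that the regressions will seriously distort the CDE effect. Fitting all 20 candidates together at N = 140 does inflate the log odds ratio by about 18% and gives an apparent AUC of 0.75 against 0.56 in new patients. No section plans such a fit. Only screened variables enter, and the resulting models average fewer than two parameters, so those figures do not describe this plan. This objection stands.

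**The interaction count.** A reader might also count 190 pairwise interactions among 20 variables and conclude that the terms outnumber the patients. Read in sequence, section 10.1 brings in interactions after screening, so they arise among the few variables that enter. This stands too.

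**The candidate count is an assumption.** Several recorded items may not be POCD predictors. Section 8.1.2 presents the EBIQ as a subjective index of cognitive change. Section 10.1 treats pain as a secondary outcome. Sections 1 and 3.3 list arterial pressure, BMI and hypertension in relation to CDE. Section 6.1 records analgesia without giving it a modelling role. This is why a range of 10 to 20 is used, and the result at 10 is clearly milder.

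**Scope.** The adequacy sentence sits with exploratory analyses that include linear models, which are limited by N. The primary comparison has its own calculation. Both points are correct and narrow the finding to the logistic models.

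**Selection, not sample size, produces the spurious terms.** The rate hardly changes between 140 and 193 patients. That is right, and it means that rewording the adequacy sentence alone would not be enough. The selection rule is nevertheless fixed in this protocol, so it is not a detail left to an analysis plan.

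**Conclusion.** The concern holds in limited form. Total N is the wrong basis for calling the logistic regressions adequate. The relevant figures are about 52–71 POCD events, and 53–73 CDE events at the planning rate or 25–35 at the 18% in section 2.

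The harm lies in which predictors are reported and how well the model seems to fit. Between about a quarter and a half of final models would carry a spurious term, and with 20 candidates apparent discrimination would be about 0.05 too high. The documents do not support a claim that the CDE odds ratio is materially biased or its variance doubled, provided CDE stays in the model. The last sentence on the final model in section 10.1 suggests that it does, but does not say so outright.

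The result rests on these assumptions: 10–20 candidates, null covariates of which about half are mildly correlated with CDE, the protocol's own rates, and 30% loss from 200 for the lower case. The improvement is worth making and cheap. It does not undermine the primary unadjusted comparison.

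**What to change.** In section 10.1:

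1. Replace the adequacy sentence with the expected events for the logistic models: about 52–71 for POCD, and for CDE 53–73 at 38% or 25–35 at 18%. State that linear models are limited by the number of participants.
2. State that CDE is kept in the POCD model whatever its p-value, with a short list of covariates named in advance on clinical grounds and sized to the events.
3. Remove the data-driven search for two-way interactions.
4. Label any further selected model exploratory, and report its fit with optimism correction, for example by bootstrap.

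Penalised (Firth) estimation and fixed caps, such as 5–7 parameters for POCD and about 3 for CDE at 18%, are optional. The caps rest on an events-per-variable convention that the protocol does not supply.

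The cost is redrafting one section and agreeing the covariate list before analysis; no new data are needed. The downside is that fewer variables are examined in one model and the stated adequacy is less favourable.
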